10.3.3. Analysis Windows and Baseline

The observational period for each subject includes the screening period (from Day -14 to Day -1), the EOS visit (Day 210 or withdrawal date). The time at which LDL-C levels have returned to >80% of baseline values will be the last observation. Any lab results collected after the last observation will not be included in the planned efficacy analysis. Safety events after the last observation, even if collected on the eCRF, will not be included in the planned statistical analysis. However, all data, including that reported after the defined observational period, will be included in the subject data listings.

Unless otherwise specified, for evaluations that are collected at multiple occasions prior to initiation of study drug, the last evaluation will be considered the "Baseline" evaluation for analysis.

Two samples for lipids and PCSK9 will be taken prior to initiation of study drug (one at screening and one prior to randomization on Day 1). The average value of the two samples will be used as the baseline evaluation.

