5.3.3. Analysis Windows and Baseline

The observational period for the study includes screening period (from Day -14 to Day -1) to the EOS visit (follow-up Visit 8, Day 210 or withdrawal date). The time at which LDL-C levels have returned to >80% of baseline values will be the last observation. Any lab results collected after the last observation will not be included in the planned efficacy analysis. Safety events after the last observation, if collected on the eCRF, will not be included in the planned statistical analysis. However, all data, including safety events that were reported after the defined observational period, will be included in the subject data listings.

Unless otherwise specified, for evaluations that are collected at multiple occasions prior to initiation of study drug, the last evaluation will be considered the "Baseline" evaluation for analysis. Two PD samples for lipids and PCSK9 will be taken prior to initiation of study drug. The average of the two samples will be used as the baseline evaluation. If only one sample was collected, the collected sample will be used as baseline. If more than two samples were taken, then the average of the last two will be used as baseline.

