5.4.4.2. Endpoints

The secondary endpoints of this trial are:

- Change from Baseline LDL-C
 - Percentage change in LDL-C from baseline to Day 90
 - Percentage change in LDL-C from baseline to Days 14, 30, 60, 120, 150, and 210
 - Proportion of subjects in each group with LDL-C greater than 80% of the baseline value at Day 180 and Day 210
 - Duration of time on treatment for subjects to return to >80% of baseline or greater LDL-C or PCSK9 protein (if not resolved by Day 210, subjects will continue to be followed until LDL-C returns to within 80% of baseline.
 - Individual responsiveness defined as the number of subjects reaching on treatment LDL-C levels of <25 mg/dL, <50 mg/dL, <70 mg/dL, and <100 mg/dL at Days 90, 120, and 180
 - Proportion of subjects in each group with greater or equal to 50% LDL C reduction from baseline at Days 90, 120, and 180
 - Proportion of subjects in each group who attain global lipid modification targets for their level of ASCVD risk

> Change from Baseline Lipids/Lipoproteins

Secondary efficacy assessments will include the measure the effects of ALN-PCSSC on levels of lipids and lipoproteins including total cholesterol, triglycerides, LDL-C (calculated and BQ) HDL-C, non-HDL-C, very low-density lipoprotein (VLDL), Apo-AI, Apo-B, Lp(a), CRP, and PCSK9.

- Percentage change in PCSK9 levels from baseline to Days 14, 30, 60, 90, 120, 150, 180, and 210
- Percentage change in other lipids, lipoproteins, apolipoproteins from baseline at each subsequent visit to Day 210

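### Two ends of observation leave the adverse-event cut-off unsettled; under one of them, safety follow-up runs longer in subjects whose response lasts

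*Protocol*

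**What the plan says.** Protocol 10.3.3 ends each subject's observational period at "the EOS visit (Day 210 or withdrawal date"). The next sentence gives a different end: "The time at which LDL-C levels have returned to >80% of baseline values will be the last observation". SAP 5.3.3 repeats both.

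The exclusions are tied to that last observation, not to the end-of-study (EOS) visit. For efficacy: "Any lab results collected after the last observation will not be included in the planned efficacy analysis". For safety, the protocol says "Safety events after the last observation, even if collected on the eCRF, will not be included in the planned statistical analysis", and the SAP says "Safety events after the last observation, if collected on the eCRF, will not be included in the planned statistical analysis". The protocol paragraph closes: "However, all data, including that reported after the defined observational period, will be included in the subject data listings". The SAP version covers all data, "including safety events that were reported after the defined observational period".

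Four other places bear on this:

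- **Follow-up after Day 210.** Under Protocol 3.1, 6 and 6.7, monthly visits continue only for subjects whose LDL-C has not recovered past the 80% mark, until it does or until Day 360. Protocol 8.2 and 8.3 continue adverse event (AE) and serious AE assessment at those visits, up to the subject's final observation.
- **Duration-of-effect endpoint.** SAP 5.4.4.2 adds: "if not resolved by Day 210, subjects will continue to be followed until LDL-C returns to within 80% of baseline".
- **AE tables.** Protocol 10.4.4.1 and SAP 5.4.5.1 count treatment-emergent AEs (TEAEs) in a double-blind treatment period that has no dates, and report them as numbers and percentages of subjects.
- **Laboratory tables.** Protocol 10.4.4.2 and SAP 5.4.5.2 plan incidence rates of potentially clinically significant values, with no time window.

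**The concern.** The two ends coincide only by chance. For a subject whose LDL-C recovers at Day 300, one gives Day 210 and the other Day 300. If the second governs the safety tables, the length of AE observation depends on how long the drug works. Subjects with a lasting response are observed longer and have more time to record a first event, and a crude percentage of subjects does not correct for that.

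SAP 5.4.4 uses efficacy and safety results together to help determine the Phase III dose(s). A longer-acting regimen could therefore look less safe than placebo, or than a shorter-acting regimen, only because it was watched for longer.

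**Working it through.** **The plan's own durations.** Inputs from Protocol 6: 14 days of screening, EOS at Day 210, last additional visit at Day 360.

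- 14 + 210 = 224 days, as stated.
- 14 + 360 = 374 days, as stated.

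**Extra AE observation if the LDL-C rule governs.**

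- Longest: 360 − 210 = 150 days; 360 / 210 = 1.71.
- Shortest, recovery at the first additional visit: 240 − 210 = 30 days; 240 / 210 = 1.14.

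**Extra laboratory draws** (central draws after the first injection, Protocol Table 3).

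| Schedule | Through Day 210 | Days 240, 270, 300, 330, 360 | Maximum |
|---|---|---|---|
| One dose (Days 14, 30, 60, 90, 120, 150, 180, 210) | 8 | 5 | 13 |
| Two doses (the same plus Day 104) | 9 | 5 | 14 |

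**Which end governs safety?**

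| Points to Day 210 | Points past Day 210 |
|---|---|
| The observational period is stated to end at EOS or withdrawal | The last-observation sentence carries no reference to Day 210 |
| Data after the observational period go to listings | The exclusions refer to the last observation, not to EOS |
| Protocol 3.1, 6, 8.2 and 8.3 tie the 80% rule to status by Day 210 | Protocol 8.2 and 8.3 carry AE and serious AE assessment to the final observation, which can be as late as Day 360 |
| Percentage-change endpoints stop at Day 210 (Protocol 3.4) | The SAP 5.4.4.2 duration endpoint needs LDL-C and PCSK9 after Day 210, so for efficacy laboratory results the last observation must be able to fall later; the next sentence applies the same cut-off to safety events |

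The left column is the stronger, but it does not remove the right. SAP section 7 declares no changes from the protocol, so the SAP does not resolve it.

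**Direction of the effect.** Let P(t) be the chance of at least one AE by day t, equal in every arm (no drug effect). Let shares sA (active) and sP (placebo) continue to day T, with continuation unrelated to AE risk. Then:

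excess in crude percentage = (sA − sP) × [P(T) − P(210)].

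P(t) cannot fall with time, so the second factor is zero or positive and the sign is that of sA − sP. Protocol 1.2.2 reports an average LDL-C reduction of about 40% at 140 days in Phase I, that is 100 − 40 = 60% of baseline, below the 80% mark. In the two-dose arms Day 210 is only 210 − 90 = 120 days after the second injection. So sA should exceed sP, and it may differ between regimens. That Phase I figure is a group mean over other doses and does not give the shares. The documents give none of sA, sP, P or T, so the formula gives a direction and no size.

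**The TEAE period.** Protocol 6 and SAP 1.4 date a Treatment Phase: Day 1 for one dose, Day 1 to Day 90 for two. Using it as the TEAE window would leave one-dose arms a single day, which cannot be intended. Nor does either document call Days 211 to 360 treatment; Protocol 6 labels them additional follow-up. The end of the TEAE period is therefore unclear.

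**Laboratory incidence.** The laboratory exclusion covers only the efficacy analysis, and the next sentence covers safety events. Neither names safety laboratory values, so no cut-off applies to the incidence tables under either reading.

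**The case against.** The best defence is that the documents, read as a whole, mean Day 210. Reporting periods in Protocol 8.2 and 8.3 run from randomization to EOS, with later visits added only in a note. The 80% rule appears elsewhere only to decide who continues past Day 210. A sensible programmer would cut at Day 210, the AE comparison would be fair, and later events would be listed. This makes the harm conditional. It does not settle the text, because the same note runs to the final observation and the duration endpoint needs a later end.

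It is also fair that safety is descriptive, that no hypothesis test is touched, and that by-visit laboratory summaries, vital signs, ECG and neurological tables do not accumulate with longer follow-up. Time to first injection site reaction is already time-based.

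A reader might infer two stronger things. The first is that the LDL-C sentence, having no lower limit, removes Day 180 values from placebo subjects who are above 80% of baseline early on. The documents do not support this. To have returned to a level presupposes a fall, the rule is tied elsewhere to status by Day 210, and both the primary endpoint and the Day 180 and Day 210 proportions above 80% need those values. The second is that the extension would inflate AE or laboratory rates by some stated number of percentage points. Any such number would rest wholly on assumed event risks, continuation shares and leaving times.

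**Conclusion.** The point holds as an unresolved conflict with a conditional consequence.

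- **If Day 210 governs:** no distortion of AE percentages.
- **If the LDL-C rule governs:** up to 150 extra days of AE observation (1.71 times) for subjects still suppressed, entering crude percentages without exposure adjustment, with an expected bias against longer-acting regimens.
- **On either reading:** the TEAE period has no clear end, and the laboratory incidence tables have no cut-off and could include up to 5 extra draws on top of 8 or 9.

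The direction assumes that continuing subjects are mainly on active drug, which the Phase I results make likely but do not quantify. AE collection after Day 210 is also not strictly nil in other subjects: Protocol 8.3 lets an investigator report later serious AEs and AEs of special interest in anyone. The harm is to the reading of safety tables that inform dose choice, not to the primary analysis. It should be settled before database lock so that the window is not chosen with data in view.

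**What to change.** 1. In Protocol 10.3.3 and SAP 5.3.3, state that LDL-C recovery above 80% of baseline ends only the additional follow-up after Day 210, and excludes no efficacy or safety data up to Day 210.
2. Define the comparative safety window as first injection through Day 210 or withdrawal in every arm. Use it for TEAEs (Protocol 10.4.4.1, SAP 5.4.5.1), in place of the undated treatment period, and for laboratory incidence (Protocol 10.4.4.2, SAP 5.4.5.2).
3. Report events on Days 211 to 360 in a separate table with person-time.
4. Keep LDL-C and PCSK9 after Day 210 for the duration-of-effect endpoint.
5. Reconcile SAP 2.4, which lists LDL-C recovery as a condition for completing the study, with Protocol 6.6, which does not.

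Cost: wording in three protocol sections and four SAP sections, and one extra table. Data through Day 210 are already collected in every arm, and the visit schedule does not change. The downside is that events on Days 211 to 360 sit outside the main between-arm comparison.

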6.3. Screening Period (Days -14 to -1)

The following procedures will be performed within 2 weeks prior to randomization:

- Informed consent
- Medical history
- Physical examination (including height and weight and full neurological examination [see [Appendix A](#)])
- Assessment of inclusion/exclusion criteria
- Vital signs
- 12-lead ECG
- HbA1c (local)
- Local clinical laboratory (hematology, chemistry [including fasting glucose, liver and renal function] and coagulation testing) (see [Appendix C](#))
- Urinalysis (local)
- Pregnancy test (local)
- Fasting lipids/lipoproteins (local)
- Concomitant medications
- Central laboratory for the following efficacy parameters: lipid panel, LDL-C by beta quantification, PCSK9, hsCRP, lipoprotein a [Lp(a)], apolipoprotein A1 [Apo-A1] and apolipoprotein B [Apo-B]) and the following safety parameters: inflammatory biomarkers, hsCRP and inflammatory markers interleukin 6 (IL6), interferon-gamma (IFN- γ) and tumor necrosis factor-alpha (TNF- α)

All local screening laboratory tests will be analyzed in-house at the participating institution's laboratory. Results must be available before the start of study drug injection on Day 1 to confirm subjects meet eligibility criteria (see [Section 4](#)). The results of all local screening laboratory tests should be reviewed prior to randomization. If these results confirm an exclusion criterion or suggest any contraindication to treatment with ALN-PCSSC, the subject must not be randomized. All Central laboratory assessments drawn during screening are not required to be reviewed prior to randomization. Please refer to [Appendix C](#) for details of laboratory tests performed during the screening period.

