6.4. Randomization

The following procedures will be performed prior to the injection:

- Assessment of inclusion/exclusion criteria

- Randomization
- Vital signs: blood pressure, heart rate, temperature, and respiration will be measured prior to injection
- 12-lead ECG
- HbA1c (central)
- Central clinical laboratory (hematology, chemistry [including fasting glucose, liver and renal function, hsCRP and inflammatory markers (IL6, IFN- γ , and TNF- α), and coagulation testing])
- Urinalysis (local)
- Pregnancy test (local) (women of childbearing potential only)
- Assessment of ADA (central)
- Central laboratory for efficacy parameters (lipid panel, LDL-C by beta quantification, PCSK9, hsCRP, lipoprotein a [Lp(a)], apolipoprotein A1 [Apo-A1] and apolipoprotein B [Apo-B])
- Concomitant medications
- AE reporting
- SAE reporting

The following procedures will be performed after the injection:

- Vital signs: blood pressure, heart rate, temperature, and respiration (4 hours after injection)
- ADA (4 hours after injection) (central)
- Concomitant medications
- AE reporting
- SAE reporting

Randomization should only occur once subject eligibility is confirmed. Randomization via an automated IWRS will be used to assign subjects to study drug. All treatment groups will be studied concurrently. A total of 480 randomized subjects are planned for inclusion in the study: 60 subjects per each of six ALN-PCSSC treatment groups plus 120 subjects total across the placebo groups (20 subjects each to match each of the six drug groups).

Study drug administration will occur at this visit for all subjects (only dose for those randomized to receive a single dose and the first of two doses for those randomized to receive two).

Study drug preparation: The pharmacist will prepare the study drug under aseptic conditions. The amount (in mL) of study drug to be administered will be determined based on the assigned dose level for the cohort. On study drug dosing days, the pharmacist or designee will withdraw the required amount of study drug into one or more syringes to be administered to the subject on

that day. The procedure for preparing study drug and the volume to be loaded into each syringe is provided in the Pharmacy Manual.

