7.2.2. Change from Baseline in Lipids/Lipoproteins

Secondary efficacy assessments will include the measure the effects of ALN-PCSSC on levels of lipids and lipoproteins including total cholesterol, triglycerides, LDL-C, HDL-C, non-HDL-C, VLDL-C, Apo-A1, Apo-B, Lp(a), hsCRP, and PCSK9.

- Percentage change in PCSK9 levels from baseline to Days 14, 30, 60, 90, 104, 120, 150, 180, and 210
- Percentage change in other lipids, and apolipoproteins from baseline at each subsequent visit to Day 210
- Proportion of subjects in each group who attain global lipid modification targets for their level of ASCVD risk

Additional aliquots of plasma and serum will be collected at each time point and stored for additional analyses, including future analysis of biomarkers of CV risk.

Plasma samples will be analyzed using a validated enzyme linked immunosorbent assay to determine PCSK9 protein concentration. Full details of the analytical methods used will be described in a separate bioanalytical report.

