APPENDIX B. SAMPSON CRITERIA FOR DIAGNOSING ANAPHYLAXIS

Anaphylaxis is highly likely when any one of the following three criteria is fulfilled:

1. Acute onset of an illness (minutes to several hours) with involvement of the skin, mucosal tissue, or both (eg, generalized hives, pruritus or flushing, swollen lips-tongue-uvula)

AND AT LEAST ONE OF THE FOLLOWING:

- a. Respiratory compromise (eg, dyspnea, wheeze-bronchospasm, stridor, reduced peak expiratory flow [PEF], hypoxemia)
- b. Reduced blood pressure or associated symptoms of end-organ dysfunction (eg, hypotonia [collapse], syncope, incontinence)

2. Two or more of the following that occur rapidly after exposure to a likely allergen for that patient (minutes to several hours):
 - a. Involvement of the skin-mucosal tissue (eg, generalized hives, itch-flush, swollen lips-tongue-uvula)
 - b. Respiratory compromise (eg, dyspnea, wheeze, bronchospasm, stridor, reduced PEF, hypoxemia)
 - c. Reduced BP or associated symptoms (eg, hypotonia [collapse], syncope, incontinence)
 - d. Persistent gastrointestinal symptoms (eg, painful abdominal cramps, vomiting)
3. Reduced blood pressure after exposure to a known allergen for that patient (minutes to several hours):
 - a. Infants and children: low systolic blood pressure (age specific) or > 30% decrease in systolic blood pressure*
 - b. Adults: systolic blood pressure <90 mmHg or >30% decrease from that person's baseline

*Low systolic blood pressure for children is age specific and defined as: <70 mmHg for age 1 month to 1 year; <70 mmHg + [2 x age] for age 1 to years; <90 mmHg for age 11 to 17 years.

Source: Sampson et al, 2005; Sampson et al, 2006.

**APPENDIX C. CLARIFICATION OF LABORATORY ASSESSMENTS
TO BE PERFORMED IN THE SCREENING PHASE (DAY
-14 TO -1)**

Screening Labs	Local / central Lab	Comments
Hematology	Local lab	Standard panel to include Hb, WBC and platelets as a minimum
Chemistry	Local lab	Standard chemistry panel to include BUN and electrolytes, serum creatinine, glucose. (Taken at same time as fasting lipids so glucose measurement is fasting). Liver function tests to include ALT, AST and total bilirubin which are exclusion criteria
Coagulation	Local lab	Standard coagulation panel to include PTT or aPTT, INR and PT (if part of local coagulation panel)
Inflammatory biomarkers	Central lab	hsCRP and inflammatory markers (IL6, IFN- γ , and TNF- α) will be measured only at the central lab
HbA1c	Local lab	HbA1c is an exclusion criteria

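### The two-sample baseline is not extended to IL6, IFN-gamma and TNF-alpha, and the plan does not settle which baseline hsCRP takes; averaging would give a modest precision gain in descriptive outputs

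*Protocol*

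**What the plan says.** **Baseline rule.** Protocol 10.3.3 states the default: "for evaluations that are collected at multiple occasions prior to initiation of study drug, the last evaluation will be considered" the baseline, unless otherwise specified. The exception follows for lipids and PCSK9, sampled at screening and before randomization on Day 1: "The average value of the two samples will be used as the baseline evaluation". SAP 5.3.3 repeats both parts ("Two PD samples for lipids and PCSK9 will be taken prior to initiation of study drug") and adds what to do with one sample or with more than two. Neither document names hsCRP or the cytokines in the exception.

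**What is sampled before dosing.** Protocol 6.3 lists, at screening, "Central laboratory for the following efficacy parameters: lipid panel, LDL-C by beta quantification, PCSK9, hsCRP", then Lp(a), Apo-A1 and Apo-B, "and the following safety parameters: inflammatory biomarkers, hsCRP and inflammatory markers interleukin 6 (IL6" and, continuing, IFN-gamma and TNF-alpha. Appendix C says of hsCRP and these three markers that they "will be measured only at the central lab". Protocol 6.4 repeats the panel before the Day 1 injection ("Central laboratory for efficacy parameters (lipid panel, LDL-C by beta quantification, PCSK9, hsCRP" and the rest) and lists hsCRP and the cytokines again under central chemistry.

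**How the results are used.** Protocol 10.4.4.2 plans changes and percent changes for laboratory values. Protocol 10.3.1 and SAP 5.3.1 report the mean and SD together with the median and quartiles. The Protocol synopsis says that secondary and exploratory analyses are descriptive.

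**The concern.** A percentage change divides by the baseline, so error in a single baseline value enters every later change for that subject. The plan accepts this argument for lipids and PCSK9 by averaging two samples. As written, it does not apply it to the cytokines, although Protocol 6.3 and 6.4 give them the same two central samples.

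hsCRP raises a second problem. Protocol 7.2.2 lists it among lipids and lipoproteins ("VLDL-C, Apo-A1, Apo-B, Lp(a), hsCRP, and PCSK9"), while Protocol 7.1.2 lists it under biochemistry. Two programmers following the text could derive different hsCRP baselines, or use one in the efficacy tables and another in the laboratory tables.

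At stake are the precision of descriptive summaries and the level of the mean percentage change. The primary LDL-C endpoint already uses the two-sample average.

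**Working it through.** **Step 1: which rule applies to which marker.**

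| Marker | Points to averaging | Points to last value |
|---|---|---|
| IL6, IFN-gamma, TNF-alpha | Nothing | Not named in the exception; Appendix C calls them inflammatory markers and omits the two-sample baseline note that it gives for lipids and PCSK9 |
| hsCRP | Listed with lipids and lipoproteins in the Protocol synopsis and 7.2.2 (as CRP in SAP 5.4.4.2); an efficacy parameter in Table 3 footnote o | Inflammatory biomarker in Appendix C; biochemistry in 7.1.2; also a safety parameter in 6.3 |
| Lp(a), Apo-A1, Apo-B | Listed with lipids and lipoproteins in 7.2.2; in the efficacy row of Table 3 | Only the endpoint wording, which names lipids, lipoproteins and apolipoproteins separately |

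So the last-value rule is clear for the cytokines, either rule can be defended for hsCRP, and averaging is the natural reading for Lp(a) and the apolipoproteins.

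**Step 2: are there two central cytokine samples?** Protocol 6.3 and Appendix C say that one is taken at screening. Protocol Table 3 footnote e lists the cytokines only from randomization onwards. The central screening panel in SAP 2.1 includes hsCRP but omits the cytokines. SAP Table 2 footnote d includes them in the clinical laboratory tests, while footnote e assigns the screening tests to the local laboratory. The second central sample is therefore planned in some places and absent or local in others.

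**Step 3: variance of change on the log scale.** The plan states no figure to reproduce. Let each measurement have log-scale error variance s², let ρ be the correlation of the two pre-dose errors, and let the follow-up error be independent of both.

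- Last value only: s²(1 + 1) = 2s².
- Two-sample average of logs: s²[1 + (1 + ρ)/2].
- Ratio at ρ = 0: 1.5/2 = 0.75, a fall of 25%.
- Ratio at ρ = 0.3: 1.65/2 = 0.825, a fall of 17.5%.
- Ratio at ρ = 0.5: 1.75/2 = 0.875, a fall of 12.5%.

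**Step 4: percentage change with no true change.** The assumptions are log-normal errors, within-subject CV of 20% to 60%, and 2,000,000 simulated subjects per setting. For a single baseline, theory gives a mean percentage change of exp(s²) − 1 = CV², that is 4%, 16% and 36% at CVs of 20%, 40% and 60%. The simulation agrees. The averaged baseline here is the arithmetic mean of the two samples.

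| CV | Mean: last / averaged ρ=0 / averaged ρ=0.3 | SD: last / averaged ρ=0 | Median: last / averaged ρ=0 |
|---|---|---|---|
| 20% | +4.0 / +2.0 / +2.6 | 29.7 / 25.2 | 0.0 / −0.9 |
| 40% | +16.0 / +8.0 / +10.3 | 68.2 / 54.2 | 0.0 / −3.5 |
| 60% | +36.1 / +17.8 / +22.7 | 125.5 / 91.1 | +0.1 / −6.8 |

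All entries are percentage points. The bias of the mean halves with independent errors. At ρ = 0.3 and CV 40% it falls by 1 − 10.3/16.0 = 36%. The median moves the other way.

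**Step 5: arm contrast.** With no effect, both arms carry the same bias and it cancels under either rule. With a true difference of −20 points in means and ρ = 0, the contrast reads −20.8 (last value) against −20.4 (averaged) at CV 20%, −23.2 against −21.6 at CV 40%, and −27.2 against −23.6 at CV 60%.

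**The case against.** The case on the other side is substantial. The last pre-dose value is a valid, prespecified baseline applied alike in every randomized arm. These markers are summarised descriptively, and the SAP's biochemistry list (5.4.5.3) names neither hsCRP nor the cytokines. Averaging with an arithmetic mean would move the median away from zero, and the median is arguably the better summary for a skewed marker. The size of the gain rests on assumed variability.

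All of this stands and keeps the point small. It does not remove the gap: the cytokines are left out of a rule that the plan already uses, and the hsCRP baseline is undefined.

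A reader might also infer three stronger things that the documents do not support.

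- That the hsCRP rule definitely discards the screening sample. The plan lists hsCRP with lipids as well as with inflammatory markers, so the fault is ambiguity. Nor does any section prescribe two different hsCRP baselines.
- That all reported changes are more biased. This holds for the arithmetic mean and, when a true effect exists, for the difference in means. It does not hold for the median or for the contrast under no effect.
- That the variance falls by 25% for every such marker. That needs independent errors in two samples taken at most about two weeks apart.

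**Conclusion.** The point holds as a low-priority improvement. Subject to the conflict over screening cytokines, IL6, IFN-gamma and TNF-alpha have two central pre-dose samples and use one; hsCRP needs a stated rule; Lp(a), Apo-A1 and Apo-B need only confirmation.

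Using the last value alone makes the log-scale variance of change 14% to 33% larger than a two-sample baseline would (1/0.875 to 1/0.75). It also leaves a larger upward bias in the arithmetic mean percentage change, about twice as large if errors are independent. These figures rest on log-normal errors, a follow-up error independent of baseline, pre-dose error correlation of 0 to 0.5 for the variance ratio, and CVs of 20% to 60% for the percentage scale. None of these comes from the documents. No confirmatory result is affected.

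**What to change.** 1. In SAP 5.3.3, and in Protocol 10.3.3 at the next amendment, extend the two-sample central baseline to hsCRP, Lp(a), Apo-A1, Apo-B, IL6, IFN-gamma and TNF-alpha. Keep the SAP's single-sample fallback.
2. State that hsCRP uses this same baseline in every table, efficacy and laboratory.
3. For hsCRP and the cytokines, average and summarise on the log scale (geometric mean of the two samples, geometric mean ratio to baseline). The average of two logs has the same expectation as one log, so under the assumptions above this avoids the downward shift of the median that an arithmetic average causes.
4. Reconcile Protocol 6.3, Appendix C and Table 3 footnote e with SAP 2.1 and SAP Table 2 footnotes d and e on whether the cytokines are measured centrally at screening. If they are not, only the Day 1 central value exists and the single-sample fallback applies to them.

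The cost is a few sentences. If the central screening samples are taken as Protocol 6.3 states, no new samples, assays or visits are needed.
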